**4.1.8       Summaries of Continuous Endpoints**

Descriptive statistics will be used to present efficacy and safety variables. For continuous variables, n, mean, standard deviation (or standard error), median, minimum, and maximum will be presented by visit when applicable.

The changes from baseline will be summarized for relevant efficacy and safety parameters and will include 95% CIs for means. The percent changes from baseline will be summarized for

selected lab parameters and will include 95% CIs for means. Summaries for continuous endpoints will also include quartiles.

#### **4.1.9 Proportion of Patients with Pre-Defined Characteristics**

Exploratory analyses of variables that represent proportions of patients (e.g. proportions of patients achieving response in CCI at Week 24 LOCF) will be performed using the logistic regression model when there are at least 5 responders in each treatment group. For proportion of responders CCI, estimates, confidence intervals, and tests will be obtained using logistic regression model with adjustment for baseline variable(s) and pooled randomization strata to accommodate composite endpoints (e.g, adjustment for baseline CCI and pooled randomization strata).

For analysis using the logistic regression model, the pooled randomization strata will be used as the adjustment factor. Patients with randomization strata in Metformin-based regimen, SU-based regimen, TZD-based regimen, and Other regimen will be pooled together as in one strata group called as “oral antidiabetic medications”. For the analysis on the proportion of patients initiating insulin therapy in patients not on insulin at the start of the study, since all patients would be in strata of “oral antidiabetic medications”, strata will be excluded in model in this analysis.

The estimated odds ratio of dapagliflozin treatment group to the placebo group will be displayed along with standard error and the 95% confidence intervals. P-values will be calculated if applicable. Raw proportions will also be displayed by treatment group. When there are less than 5 responders in each treatment group, the unadjusted (and difference) proportions, exact 95% confidence interval, and p-values from the Fisher’s exact test (when applicable) will be provided. Although p-values will be generated for exploratory endpoints, statistical significance will not be inferred and claims will not be made.

#### **4.1.10 Summaries of Shifts from Baseline in Categorical Variables**

Changes from baseline in certain categorical variables will be summarized using shift tables. Frequencies and percents of patients within each treatment group will be generated for levels of cross-classifications of baseline and the on-treatment value of the variable. The on-treatment value can be either the value at a certain time point, (for example, laboratory tests) or the minimum/maximum value in the direction of toxicity, which has been observed during a study period. Treatment group differences will not be assessed in summaries of shifts.

#### **4.1.11 Kaplan-Meier Curve and Estimates for Time-To-Event Analyses**

Kaplan-Meier plots (Kaplan EL and Meier P 1958) will be used to generate product-limit estimates of probabilities for CCI by treatment for the 24-week double-blind period. Estimated probabilities will be displayed by treatment group as “overlay curves”. Probabilities will be connected to form a “survival curve” across rescue times and the last rescue will be carried-forward to Week 24. Additionally, a summary table will accompany the plot and will display the Kaplan-Meier estimates of the cumulative proportion (with 95% CI calculated based on Greenwood’s

method when applicable (Greenwood M 1926)) of patients with event at specific time points by treatment group. If the estimated lower bound of 95% CI is below 0 or the estimated upper bound of 95% CI is over 1, then it will be restricted to 0 or 1 respectively. Unless otherwise specified, the plot will be presented only when there are at least 5 events in one treatment group.

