Each patient’s baseline insulin therapy should remain unchanged wherever possible throughout the double-blind treatment period. The stable insulin regimen aims to continue insulin as it was being used by the patient at enrollment and lead-in, with no changes to insulin type and with as few changes in insulin dosage as possible. A stable insulin regimen is pivotal, because it makes it possible for the study to measure any differences in glycemic control between the dapagliflozin treatment arm and the matching placebo arm. Down-titration of insulin will be allowed only as necessary to prevent low blood glucose or hypoglycemia. During the double-blind treatment period, a few patients will experience poor glycemic control, as measured by increased FPG measurements from the central laboratory during study visits. When glucose measurements exceed certain limits (as specified in [Table 2](#) above), the patient will be “rescued”.

During the double-blind treatment period, if up-titration of insulin dose is $>10\%$ (lasting more than 7 consecutive days) in comparison to the mean daily insulin dose at baseline, the patient shall be handled as administration of anti-diabetic rescue medication (i.e., the patient must complete the Week 24 visit procedures, as outlined in section [4.3.5](#)) and the patient will continue in the treatment period according to their original visit schedule. Patients must record the daily dose of insulin in the diary provided (minimum of 80% of days with a value) and review any changes in insulin doses with their investigator, either at regularly scheduled visits, or via telephone calls between visits. Patients required to be rescued, shall be called for an unscheduled visit within 5 days, to complete the Week 24 procedures.

Any insulin dose changes (even if more than $\pm 10\%$ of the mean daily insulin dose at baseline) is not considered as an up or down titration as long the insulin dose change is not for a period of more than 7 consecutive days. For example, dose changes due to known changes in physical activity or food intake will not be registered as up or down titration as long as the insulin dose is back to the previous dose after the change. Similarly, if insulin requirement has increased temporarily, e.g., due to an infection, it will not be considered an up-titration even if the insulin dose increase is more than 10% of the baseline mean daily insulin dose, as

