8.5.6 Exploratory analysis

Exploratory analysis on continuous exploratory endpoints will be evaluated using a MMRM, similar to the one used for the primary analysis of the primary endpoint. Exploratory subgroup analysis will include additional covariates and interaction terms for the subgroup variables.

CCI

Exploratory analyses of variables that represent proportions of patients will be performed using the logistic regression with adjustment for randomization strata and baseline measurement.

Exploratory analyses of time-to-event variables will be performed using Kaplan-Meier plots accompanied by a tabular summary.

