**Table 4 Lack of Glycemic Control Criteria for Initiation of Open-Label Rescue Medication**

Visit Label	Central Laboratory FPG
From Week 4 (Visit 6) to Week 12 (Visit 7) (excluding Week 12)	FPG >240 mg/dL (13.3 mmol/L)
From Week 12 (Visit 7) to Week 24 (Visit 8) (excluding Week 24)	FPG >200 mg/dL (11.1 mmol/L)

Patients with a central laboratory FPG value meeting the lack of glycemic control criterion at a pre-specified visit will be scheduled for a follow-up visit (within 3 - 5 days) to obtain a second central laboratory FPG value and review the patient's glucose meter readings. If the repeat central laboratory FPG value still meets the criterion, the patient will receive rescue medication.

Irrespective of study visit number, patients who meet rescue criteria in the treatment period must first complete the Week 24 visit's procedures before receipt of open-label anti-diabetic rescue medication to ensure that important study endpoint measurements are collected.

Following completion of the Week 24 “Rescue” visit, rescued patients will be administered open-label rescue medication in addition to their blinded study drug. Rescued patients will then continue in the treatment period according to their original visit schedule. Patients who received a first open-label anti-diabetic rescue medication, who subsequently fulfill lack of glycemic control criteria described in the [Table 4](#) above, may have other rescue medications added or substituted, according to Investigator judgment, without repetition of rescue visits.

Patients with a central laboratory FPG value >200 mg/dL (11.1 mmol/L) at Week 24 (Visit 8), will not be considered as rescued for efficacy analysis.

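### The Kaplan-Meier rescue table uses untransformed Greenwood limits cut off at 0 and 1, which sit too low when an arm has few events; log-log limits plus a zero-event rule would be more accurate

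*SAP*

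**What the plan says.** SAP section 4.1.11 plans Kaplan-Meier curves by arm over the 24-week double-blind period, with a table of cumulative proportions at specific time points. The name of the event is blacked out, but the curve is drawn "across rescue times and the last rescue will be carried-forward to Week 24", so the event is evidently rescue.

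The table is to be shown "with 95% CI calculated based on" Greenwood's method, when applicable. No transformation is named. A repair rule covers one case: "If the estimated lower bound of 95% CI is below 0 or the estimated upper bound of 95% CI is over 1". Such a limit is moved to the nearer boundary. Nothing is said about the interval when an arm has no events at a time point.

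The display is conditional: "the plot will be presented only when there are at least 5 events in one treatment group". The table accompanies the plot.

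Neither document gives an expected rescue rate. Protocol section 4.3.3.1 says only that "a few patients will experience poor glycemic control". Protocol section 8.5.6 sets the status of the analysis: "Exploratory analyses of time-to-event variables will be performed using Kaplan-Meier plots accompanied by a tabular summary".

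**The concern.** Log-log limits cannot leave the range 0 to 1, so a rule for limits that do leave it implies the plain interval, estimate ± 1.96 × standard error. For a small proportion that interval is symmetric where the sampling distribution is skewed. It therefore sits too low. The lower limit can print as 0% in an arm where patients were rescued, and the upper limit understates how high the rate could be.

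The five-event condition limits this but does not remove it. It is met when one arm reaches five events, so the other arm may have fewer. Early rows may also be sparse, because the rescue criteria in SAP Table 4 start only at Week 4 and use the higher glucose threshold until Week 12.

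What is at stake is the accuracy of the error bars in one descriptive table.

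**Working it through.** **Inputs.** 151 randomized per arm (SAP 1.4). Rescue rate: not stated, so true rates of 0.5% to 20% per arm are assumed. No censoring before the time point is also assumed, for simplicity; Greenwood's variance then equals the binomial variance.

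**The plan's own sample size.** Normal approximation: 2 × (1.960 + 0.842)² × 0.9² / 0.3² = 141.3, so 142 per arm. The exact two-sample t-test gives 142.25, so 143, with 80.2% power. Allowing for 5%: 143 / 0.95 = 150.5, so 151 per arm and 302 in total. The stated figures reproduce.

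**Formulas.** With d events, p = d/n, S = 1 − p and se = √(pS/n):
- plain: p ± 1.96 × se, cut off at 0 and 1
- log-log: 1 − S^exp(∓1.96v), with v = se / (S × |ln S|)

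Example, d = 5: p = 0.0331 and se = 0.01456, so the plain limits are 0.46% and 6.17%. With |ln S| = 0.03367, v = 0.4472 and the log-log limits are 1.39% and 7.77%.

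**Limits at n = 151 (%), plain limits shown before the cut-off**

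| Events | Estimate | Plain | Log-log | Exact (Clopper-Pearson) |
|---|---|---|---|---|
| 0 | 0.00 | 0.00 to 0.00 | undefined | 0.00 to 2.41 |
| 1 | 0.66 | −0.63 to 1.96 | 0.09 to 4.61 | 0.02 to 3.63 |
| 2 | 1.32 | −0.50 to 3.15 | 0.33 to 5.19 | 0.16 to 4.70 |
| 3 | 1.99 | −0.24 to 4.21 | 0.65 to 6.03 | 0.41 to 5.70 |
| 4 | 2.65 | 0.09 to 5.21 | 1.00 to 6.90 | 0.73 to 6.64 |
| 5 | 3.31 | 0.46 to 6.17 | 1.39 to 7.77 | 1.08 to 7.56 |
| 15 | 9.93 | 5.16 to 14.70 | 6.11 to 15.94 | 5.67 to 15.85 |
| 30 | 19.87 | 13.50 to 26.23 | 14.34 to 27.17 | 13.82 to 27.13 |

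The lower cut-off therefore acts at 1, 2 or 3 events and not from 4 upward.

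**Coverage.** For each true rate, sum the binomial probabilities of the counts whose interval contains it. For log-log alone, zero events counts as a miss. With an exact limit at zero events (upper limit 1 − 0.025^(1/151) = 2.41%), the zero-event probability is added back for true rates below 2.41%: at 1%, 71.5 + 21.9 = 93.4.

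| True rate | Plain coverage | Truth above / below plain interval | Zero events | Log-log alone | Log-log with zero rule |
|---|---|---|---|---|---|
| 0.5% | 53.1% | 46.9 / 0.0% | 46.9% | 49.0% | 95.9% |
| 1% | 78.0% | 21.9 / 0.1% | 21.9% | 71.5% | 93.4% |
| 2% | 80.3% | 19.3 / 0.4% | 4.7% | 92.0% | 96.7% |
| 3% | 93.7% | 5.7 / 0.6% | 1.0% | 95.1% | 95.1% |
| 5% | 93.8% | 5.3 / 0.9% | about 0 | 95.6% | 95.6% |
| 8% | 91.3% | 7.7 / 0.9% | about 0 | 95.1% | 95.1% |
| 10% | 92.7% | 5.7 / 1.5% | about 0 | 95.9% | 95.9% |
| 20% | 94.5% | 3.4 / 2.1% | about 0 | 94.7% | 94.7% |

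The nominal miss is 2.5% on each side.

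**Does the five-event rule protect the table?** Given that the plot is shown, the chance that an arm has 3 or fewer events at Week 24 is 64% for true rates of 2% and 5% in the two arms, 33% for 3% and 8%, 9% for 5% and 5%, 5% for 5% and 10%, and about 0% for 10% and 20%.

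**The case against.** **No low rate is documented.** A reader might infer that low event rates are expected and that the table will be visibly wrong. The documents do not support that. They speak only of a few patients, with no figure. At 5% or more the plain upper limit is about 1 to 1.6 points below the log-log one, coverage is about 91% to 94.5%, and the cut-off rarely acts at Week 24. This stands, and the point rests on an assumed range.

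**The worst figures often describe a table that is not shown.** At a true 2%, an arm reaches five events 18.6% of the time. If both arms are at 2%, the display appears in 1 − 0.814² = 34% of trials. The coverage figures above do not condition on display. This stands in part: with unequal arms a sparse arm is still shown, and so are sparse early rows.

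**Log-log limits alone are not a free cure.** A reader might infer that switching scale is enough. It is not. At zero events Greenwood's variance is 0 and the log-log limits are undefined, and at 0.5% and 1% log-log alone covers less than plain. Log-log also errs slightly upward: at 3% to 5% it lies wholly above the truth about 4% of the time. The first part stands fully and is why a zero-event rule is needed. The second is a smaller error than the one it replaces.

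**The table carries little weight.** It would be wrong to read it as the only account of rescue by arm: SAP 4.2.5.1 also summarizes rescue use by treatment group and lists every rescued patient. Section 4.1.11 specifies no test between arms. Cut-off plain limits are a recognized convention, and the plan is not contradictory. All of this stands and sets the importance. On the other side, SAP 4.1.9 already turns to exact intervals for sparse responder counts, while 4.1.11 has no such provision.

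**Conclusion.** The point holds as a minor improvement. The planned interval sits too low at small counts: at 1 to 3 events it prints a lower limit of 0 although events occurred, and at zero events it prints 0 to 0. Coverage is about 78% to 80% at true rates of 1% to 2% and about 91% to 94.5% from 3% to 20%, with misses mostly on the upper side. These figures assume 151 per arm, no censoring and a range of rescue rates that the documents do not state.

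A reader might go further and infer that the trial's conclusions are affected. They are not: the table is descriptive and exploratory, and no primary or secondary test, error rate or sample size changes.

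**What to change.** In SAP section 4.1.11:
- state that the 95% limits are complementary log-log transformed, with Greenwood variance;
- add that when an arm has zero events at a time point, the lower limit is 0 and the upper limit is the exact Clopper-Pearson limit (2.4% at 0/151), and name the denominator to be used if patients have been censored by then;
- delete the sentence that cuts limits off at 0 and 1.

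Coverage at the tabulated true rates is then 93.4% to 96.7%.

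The cost is a sentence or two in the SAP, one procedure option and one extra rule to program for zero-event cells. Upper limits will be slightly higher than under the current text: 7.8% instead of 6.2% at 5 events, and 15.9% instead of 14.7% at 15.

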#### **4.1.12 eGFR**

eGFR is calculated according to the MDRD formula:  $GFR (mL/min/1.73m^2) = 175 \times (\text{standardized sCr})^{-1.154} \times (\text{Age})^{-0.203} \times (0.742 \text{ if female}) \times (1.212 \text{ if Black})$  [Note: sCr reported in mg/dL].

## **4.2 Analysis Methods**

### **4.2.1 Patient Disposition**

All patients enrolled (who signed informed consent) will be summarized. The disposition of patients for the lead-in period, the double-blind treatment period and the whole study which include follow-up period will be summarized.

The summary of status in the lead-in period will include all patients receiving at least one dose of study drug (placebo) during the lead-in period. The summary of status in the double-blind treatment period will include all patients in Randomized Data Set. The number and percent of patients who entered, completed and discontinued, with the reasons for discontinuation will be summarized for each period (lead-in, double-blind treatment and the whole study which includes follow-up period). Summaries of double-blind and the whole study which includes follow-up period will be made by treatment group and overall.

A listing of patients who discontinued from the lead-in period and from the double-blind treatment period will be provided.

Patients enrolled, randomized, and treated will be summarized by country and study site.

### **4.2.2 Demographics and Baseline Characteristics**

Demographic and other baseline characteristics, including diabetes-related characteristics and renal function characteristics will be summarized by treatment group and overall, using the Randomized Data Set.

Demographic and baseline characteristics are listed in [Table 7](#). Diabetes related baseline characteristics are listed in [Table 8](#). Common renal function baseline characteristics are listed in [Table 9](#).

**Table 7 Demographic and baseline characteristics**

Characteristic	Summarized as	Categories
Gender	Categorical	Male, Female
Age	Categorical and Continuous	<65 yrs ≥65 yrs
Female Age	Categorical	≤50 yrs >50 yrs
Race	Categorical	White Black or African American Asian Native Hawaiian or Other Pacific Islander American Indian or Alaska Native Other
Ethnicity	Categorical	Hispanic or Latino Not Hispanic or Latino
Body weight	Continuous	--
CCI	Continuous	--
Body Mass Index	Categorical and Continuous	<25 kg/m  ≥25 kg/m  ≥27 kg/m  ≥30 kg/m 
Geographic Region	Categorical	As defined in Appendix B

**Table 8 Diabetes-Related Baseline Characteristics**

Characteristic	Summarized as	Categories
Duration of type 2 diabetes	Categorical and Continuous	<3 yrs ≥3 and ≤10 yrs >10 yrs
HbA1c	Categorical and Continuous	<8% ≥8-<9% ≥9-<10% ≥10%

**Table 8 Diabetes-Related Baseline Characteristics**

Characteristic	Summarized as	Categories
FPG	Categorical and Continuous	<110 mg/dL $\geq 110$ - <150 mg/dL $\geq 150$ - <200 mg/dL $\geq 200$ - <240 mg/dL $\geq 240$ - <300 mg/dL $\geq 300$ mg/dL
pre-enrolment anti-hyperglycemic therapy	Categorical	Insulin-based regimen SU-based regimen TZD-based regimen Metformin-based regimen other regimen

**Table 9 Baseline Renal Function Characteristics**

Characteristic	Summarized as	Categories
eGFR (MDRD)	Categorical and Continuous	<30 mL/min/1.73 m  $\geq 30$ and <45 mL/min/1.73 m  $\geq 45$ and <60 mL/min/1.73 m  $\geq 60$ and < 90 mL/min/1.73 m  $\geq 90$ mL/min/1.73 m 

All summaries of continuous characteristics will be based on non-missing observations. Summary statistics including mean, median, SD, the first and third quartiles will be calculated. For categorical characteristics, percents will be calculated out of the total number of patients in the data set, overall and by treatment group (ie, each denominator includes the number of patients with missing/unknown values for the endpoint).

Duration of Type 2 diabetes is calculated as the number of years from Type 2 diabetes diagnosis date to informed consent date:

$$(\text{consent date} - \text{diagnosis date} + 1) / 365.25.$$

The duration of diabetes will be included in the baseline diabetes characteristics listing. If the date Type 2 diabetes was diagnosed is partially missing, the following rules will take effect:

- Missing day, but month and year are present: the day will be imputed as the 15th day of the month.
- Missing day and month, but year is present: the day and month will be imputed as 30 June of the year.
- Missing year, but day and month are present: No imputations will occur, and the patient will be excluded from all summaries related to duration of Type 2 diabetes.
- Missing day, month and year: No imputations will occur, and the patient will be excluded from all summaries related to duration of Type 2 diabetes.

If any such imputed date falls after the consent date, then the diagnosis date will be taken as equal to the consent date.

Demographic and baseline diabetes characteristics will be presented in listings for each patient in the Randomized analysis set.

#### **4.2.3 Specific and General Disease Histories**

The numbers and percents of patients with diabetes history, general medical history findings and surgical history will be summarized by body system for each treatment group and overall using the Randomized Analysis Set.

For these displays, percents will be calculated out of the total number of patients in the data set, overall and by treatment group (i.e., each denominator includes the number of patients with missing/unknown values for the endpoint).

The specific disease history and general medical history will be presented in listings for each patient in the Randomized Analysis Set.

#### **4.2.4 Current and Concomitant Medications**

Current and concomitant medications will be summarized using the Safety analysis set by drug class (anatomic class and therapeutic class), generic drug name and treatment group, as defined by the AstraZeneca Drug Dictionary most current at time of database lock. A summary will be produced for each of the following:

- all current medication
- all concomitant medication
- all concomitant diuretic medication
- all concomitant ARB and/or ACE-I medication
- all concomitant anti-hypertensive medication

Current medications are defined as medications with a start date prior to the first day of double-blind treatment period and without a stop date prior to the consent date, i.e. current

medication will be any medication with at least 1 dose taken on or after the day of consent date up to the day prior to the first dose of study medication.

Concomitant medication during the double-blind treatment period is defined a medication with either

- a recorded medication start date falling within the double-blind treatment period, or
- a recorded medication start date prior to the first day of study medication during the double-blind treatment period without any recorded medication stop date prior to the start of the double-blind treatment period.

This means that concomitant medications for the double-blind treatment period will be any medication taken from start of the double-blind treatment period up to the end of the double-blind treatment period.

Missing and partial date handling of start and stop dates of previous, current and concomitant medications, is described in Section 4.3.6.

